6.2 Efficacy

6.2.1 Primary Efficacy Variable

[figure not shown]
The primary efficacy analysis is the evaluation of serum T concentration at Day 28.

6.2.2 Secondary Efficacy Variables

Secondary efficacy analyses include the evaluation of the following variables:

- T (Total)
- LH
- FSH
- PSA

All these variables will be assessed at the timepoints shown in Table 9.

Page 46 of 84

Table 9: Timepoints for Efficacy Variables

Stage	Group	Timepoint		Vai	riables		
			Local	Central	LH	FSH	PSA
			T	T			
		Baseline (pre-dose)		•	•	•	•
		24 hours post-dose		•	•	•	
		48 hours post-dose		•	•	•	
Stage 1	1 and 2	72 hours post-dose		•	•	•	
Stage	1 and 2	Day 4		•	•	•	
		Day 7		•	•	•	•
		Day 14		•	•	•	•
		Day 21 ^a	•	•	•	•	•
		Day 28		•	•	•	•
		Day 35	•	•	•	•	•
		Day 42		•	•	•	•
		Day 77	•				
Stage 2	1 and 2	Day 84		•	•	•	•
		Day 119	•				
		Day 126		•	•	•	•
		Day 161	•				
		Day 168		•	•	•	•
		Day 203	•	•	•	•	•
		Day 210	•	•	•	•	•
		Day 217	•	•	•	•	•
		Day 224 ^b	•	•	•	•	•
Stage 3	2 only	Day 231 ^b	•	•	•	•	•
		Day 238 ^b	•	•	•	•	•
		Day 245 ^b	•	•	•	•	•
		Day 252	•	•	•	•	•
		Follow up visit	•	•	•	•	•

FSH=follicle stimulating hormone; LH=luteinising hormone; PSA=prostate-specific antigen; T=testosterone

 $^{^{\}rm a}$ If PSA is ${<}0.06$ ng/mL, hs PSA will be measured and reported. If PSA is ${\geq}0.06$ ng/mL then hs PSA will not be measured and reported.

^bWeekly assessments from Day 203 until Day 252 or until serum T levels are ≥1 ng/mL (local lab result), whichever occurs first

6.3 Safety

6.3.1 Vital Signs

Vital signs parameters will be measured at screening, baseline (Day 0), and Day 28 for both Groups 1 and 2. During Stage 2 these assessments will be performed on the day of the maintenance dose. In both groups this will occur at Days 42, 84, 126, and 168 and follow-up. These vital signs will be measured with the participant in sitting position for at least 5 minutes.

In the clinic, measurements of the vital signs described below will be made by a trained and authorised person:

- Systolic BP (mmHg)
- Diastolic BP (mmHg)
- Heart rate (bpm)
- Respiratory rate (breaths per minute)
- Body temperature (°C)

The investigator will evaluate any worsening in vital signs for its clinical relevance as to whether it meets the definition of an AE (see Section 6.3.7). All changes in vital signs that meet the definition of an AE must be documented as an AE in the eCRF.

A manual or automated sphygmomanometer will be used to measure systolic and diastolic BP. BP results will be recorded in mmHg. Pulse rate will be measured in the radial artery for 60 seconds and will be recorded as beats per minute. If possible, BP and pulse rate should preferably be measured in the same arm at each visit.

Weight will be measured while the participant is clothed with shoes off and recorded in kilograms (kg).

Height will be measured in centimetres at the screening visit (Visit 1) only.

6.3.2 Physical Examination

A physical examination will be performed at the timepoints specified in Table 15, Error: Reference source not found, and Error: Reference source not found. Any abnormalities must be specified in the eCRF and, if observed after administration of teverelix TFA, the abnormality must also be documented as an AE (see Section 6.3.7).

The complete physical examination will consist of evaluation of general appearance, the skin, head, eyes (including size and reactivity of the pupils), ears, nose, throat, neck, thyroid, lungs, heart, lymph nodes, abdomen, and extremities (to include deep tendon reflexes, clonus, and muscle rigidity). Any abnormalities noted should be described.

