1.1.2 Presentation of Advanced Prostate Cancer

Advanced prostate cancer results from any combination of lymphatic, blood, or contiguous local spread. Manifestations of metastatic and advanced disease may include the following:

- Anaemia
- Bone marrow suppression

NTEV

Page 27 of 84

- Weight loss
- Pathologic fractures
- Spinal cord compression
- Pain
- Haematuria
- Ureteral and/or bladder outlet obstruction
- Urinary retention
- Chronic renal failure
- Urinary incontinence
- Symptoms related to bony or soft-tissue metastases

Treatment-related symptoms (sometimes associated with radiation therapy), such as rectal bleeding, gross haematuria, and urethrorectal fistula, need to be differentiated from the disease-specific symptoms.

Physical examination findings of adenopathy, lower-extremity oedema, and bony tenderness may indicate metastatic disease. In addition, obliteration of the lateral sulcus or seminal vesical involvement found during rectal examination often indicates locally advanced disease. Neurologic examination, including determination of external anal sphincter tone, should be performed to help detect possible spinal cord compression.

1.1.3 **Treatment Overview**

Several treatment options exist for different stages of prostate cancer, including observation, prostatectomy, radiation therapy, chemotherapy, and hormone therapy. Hormone therapy has evolved from the use of oestrogens to gonadotropin-releasing hormone (GnRH) agonists and recently, investigational GnRH antagonists [6].

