4.2 Participant Exclusion Criteria

If any of the following criteria apply, the participant MUST NOT be admitted to the study. The participant:

1. Has abnormal screening and/or baseline laboratory values that suggest a clinically significant underlying disease, or the following laboratory values:

- a. Liver function test (aspartate aminotransferase [ASAT/SGOT], alanine aminotransferase [ALAT/SGPT]), or total bilirubin exceeding twice the upper limit of the normal (ULN) range
- b. Creatinine twice the ULN range
- c. Uncontrolled diabetes (HbA1c >7.5%) or previously undiagnosed diabetes mellitus with HbA1c >6.5%
- 2. Has any contraindication to the use of teverelix TFA
- 3. Has a life expectancy of less than 1 year
- 4. Has T levels <2.0 ng/mL at screening
- 5. Has a medical history of bilateral orchidectomy
- 6. Using any of the following prohibited treatments:
 - a. Within 25 weeks prior to screening: dutasteride
 - b. Within 12 weeks prior to screening: finasteride
 - c. Current use of any of the following:
 - i. Anti-androgen therapy, including T replacement therapy and 5α -reductase inhibitor treatment etc. (Spironolactone is a permitted concomitant treatment)
 - ii. Any other medication or herbal product that may affect hormone levels and might, therefore, confound interpretation of the study results (e.g. St. John's wort)
- 7. Has neurological disease, psychiatric disease, drug or alcohol abuse, which could interfere with the participant's proper compliance
- 8. Has a history of myocardial infarction, unstable symptomatic ischaemic heart disease, any ongoing cardiac arrhythmias of grade >2 (chronic stable atrial fibrillation on stable anticoagulant therapy is allowed), thromboembolic events (e.g. deep vein thrombosis, pulmonary embolism, or symptomatic cerebrovascular events), or any other significant cardiac condition (e.g. pericardial effusion, restrictive cardiomyopathy) within 6 months before screening
- 9. Has congenital long QT syndrome or ECG abnormalities at screening of:
 - a. Q-wave infarction, unless identified ≥6 months before screening
 - b. Fridericia corrected QT interval (QTcF interval) >480 msec. If QTcF is prolonged in a participant with a pacemaker, the participant may be enrolled in the study upon discussion with the project clinician

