6.3.3 Triplicate 12-Lead Electrocardiogram

At screening (Visit 1), 12-lead ECG recordings will be obtained in triplicate (within an approximate 2- to 5-minute window) with the participant in a supine position, suitably rested (for at least 5 minutes). At baseline (Visit 2), 12-lead ECGs will be performed in triplicate before administration of the first dose of the IMP; the results should be reviewed by **the cardiologist at the site delegated to review all study ECGs (ie the rater)** to confirm that the participant may be dosed (see Exclusion Criterion Number 8).

Subsequently, triplicate 12-lead ECGs (within an approximate 5-minute window) will be obtained at each dosing visit and at the follow-up visit.

All 12-lead ECGs, including those performed at screening, will be of at least 10-second duration.

The confirmation of the decision regarding the participant's eligibility for the study and all ECGs are to be based on local readings. For evaluation of participants with left bundle branch block, a cardiology consultation is strongly recommended.

At a minimum, interval data (QTcF), ventricular rate, and overall interpretation will be reported for each ECG.

The investigator will record on the eCRF whether the results are normal or abnormal (not clinically significant or clinically significant). If recorded as abnormal and clinically significant, the machine-read results and any clinical interpretations must be incorporated into the eCRF, and, if observed after administration of teverelix TFA, the abnormality must also be documented as an AE (see Section 6.3.7).

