6.3.7 Adverse Events

All AEs, including intercurrent illnesses or pathological changes in laboratory values, must be reported and documented in detail including the time of start and end of onset and the outcome. The measures taken will be documented in the eCRF as well as intensity, relationship to study medication and seriousness of the AE.

6.3.7.1 **Definition of Adverse Events**

An AE is any untoward medical occurrence in a participant or clinical investigation participant who is administered a pharmaceutical product. This untoward medical occurrence does not necessarily have a causal relationship with the administered treatment. An AE can, therefore, be defined as any unfavourable and unintended sign (including abnormal laboratory findings), symptom, or disease that is temporally associated with the use of a medicinal (investigational) product, whether or not related to that medicinal (investigational) product. If, during treatment with an investigational product, pathological laboratory values occur which were not present before the treatment started, further clinical or laboratory tests must be

carried out until the values return to the normal range or until a plausible explanation is found (e.g. concomitant disease) for the change in the laboratory values.

Symptoms or clinically significant laboratory or instrumental (e.g. electrocardiographic) abnormalities of a pre-existing condition, such as cancer or other diseases, should not be considered an AE. However, occurrence of new symptoms, laboratory, or instrumental abnormalities, as well as worsening of pre-existing ones, are considered AEs.

Laboratory values outside the normal laboratory-specific reference range, which make an intervention necessary and/or are considered clinically significant by the investigator must be reported as AEs. If the abnormal laboratory value is a sign of a disease, only this diagnosis should be reported as an AE.

An AE is considered to be an adverse drug reaction (ADR) if a causal relationship between a medicinal product and an AE is at least a reasonable possibility.

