### **4.3 Other Measures**

#### **4.3.1 Physical Examination**

A physical examination will be performed at the timepoints specified in **Error! Reference source not found..**

Any abnormalities must be specified in the eCRF and, if observed after administration of teverelix TFA, the abnormality must also be documented as an AE (see Section 5.3.2.3). The complete physical examination will consist of evaluation of general appearance, the skin, head, eyes (including size and reactivity of the pupils), ears, nose, throat, neck, thyroid, lungs, heart, lymph nodes, abdomen, and extremities (to include deep tendon reflexes, clonus, and muscle rigidity).

Any abnormalities noted should be described.

---

Document:

C:\ProgramData\activePDF\Temp\DocConverter\API\Input\\$651f4dc0b253\$FE3041C5883446E892B20AB6D3F0E1BD.docx

Author: [name]

Version and Date: Version 1.0, 21 Apr 2023

Page 43 of 66

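### Protocol 6.3.3 (SAP 4.2.7) makes any clinically significant ECG abnormality seen after dosing an AE even if unchanged from baseline, contradicting 6.3.7.1; 6.3.2 (SAP 4.3.1) has the same gap for physical findings

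*Protocol*

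**What the plan says.** **ECG rule.** Protocol 6.3.3 has the investigator classify each ECG. "If recorded as abnormal and clinically significant, the machine-read results and any clinical interpretations must be incorporated into the eCRF" and, in the same sentence, an abnormality seen after dosing must be documented as an AE. SAP 4.2.7 repeats this.

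**Physical-examination rule.** Protocol 6.3.2 says of any abnormality: "if observed after administration of teverelix TFA, the abnormality must also be documented as an AE". SAP 4.3.1 repeats this.

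**AE definition.** Protocol 6.3.7.1 covers symptoms and clinically significant laboratory or instrumental findings, giving electrocardiographic ones as its example. It says that "abnormalities of a pre-existing condition, such as cancer or other diseases, should not be considered an AE". It then adds that new symptoms and new laboratory or instrumental abnormalities, "as well as worsening of pre-existing ones, are considered AEs".

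**Vital-signs rule, for contrast.** Protocol 6.3.1 reads: "The investigator will evaluate any worsening in vital signs for its clinical relevance as to whether it meets the definition of an AE".

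**Who is enrolled.** Under Protocol 4.2, exclusion criterion 8, "chronic stable atrial fibrillation on stable anticoagulant therapy is allowed". Criterion 9 admits Q-wave infarction identified at least 6 months before screening. Protocol 1.1.2 notes of the study disease: "Physical examination findings of adenopathy, lower-extremity oedema, and bony tenderness may indicate metastatic disease".

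**The concern.** The ECG and examination rules turn on when a finding is seen. The AE definition turns on whether it is new or worse. A man with a stable abnormality at entry gets opposite answers from two sections of one protocol, and sites can reasonably follow either.

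What is at stake is the safety report. The trial has no control arm, so there is no comparator AE rate against which an excess of carried-over baseline findings would stand out. New cardiovascular events are named in the objectives, so spurious cardiac AE entries would fall where readers will look.

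**Working it through.** The plan states no figure to reproduce. The check is a comparison of texts, followed by one illustration on an assumed rate.

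**1. One case through both rules.** Take a man whose ECG is recorded as abnormal and clinically significant at screening and Day 0, and is the same at Day 28.
- Protocol 6.3.3: abnormal, clinically significant, observed after dosing. It must be documented as an AE.
- Protocol 6.3.7.1: an electrocardiographic abnormality of a pre-existing condition, neither new nor worse. It should not be considered an AE.

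Both cannot be followed. The clash is direct because 6.3.7.1 names electrocardiographic findings and clinical significance.

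**2. The same case for an examination finding.** Persisting adenopathy is an AE under 6.3.2. Section 6.3.7.1 speaks of symptoms, laboratory findings and instrumental findings, and does not name examination signs. The conflict here is with its new-or-worsened principle rather than with its exact words.

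**3. Whether the cross-references resolve it.** Protocol 6.3.2 and 6.3.3 both end with a pointer to Section 6.3.7, but as a reference after an instruction that says must. Section 6.3.1 shows the other construction: worsening is assessed, and meeting the AE definition is the condition. In the SAP the pointers go elsewhere: 4.3.1 cites 5.3.2.3, which imputes missing AE dates, and 4.2.7 cites 6.9.2, which lists AE summaries. The SAP's own AE definition (4.2.2) omits the exception for pre-existing conditions.

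**4. Which tables are reached.**
- *All AEs* (SAP 6.9.2): reached whatever the onset date, since this line is not restricted to treatment-emergent events.
- *Treatment-related AEs* (SAP 6.9.2): possibly reached. SAP 4.2.3 classes Unlikely as related, and SAP 5.3.2.3 imputes missing causality as related.
- *Treatment-emergent AEs*: SAP 4.2.3 requires the event to be new or worsening. An unchanged finding given its true pre-dose onset drops out. It enters only if onset is placed after dosing. Dating it to the visit would do this, since Protocol 8.1.5 admits any AE occurring on or after the first-dose date. So would an onset date too incomplete to place, which Protocol 8.1.6 classes as treatment-emergent. Protocol 6.3.7.2 gives an onset rule for laboratory changes but none for an unchanged ECG or examination finding.

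**5. Size, as an illustration only.** Planned Group 2 enrolment is 60 (Protocol 3.1). The documents give no rate of persisting baseline abnormalities; assume 5% to 20%.
- 60 × 0.05 = 3 men
- 60 × 0.20 = 12 men

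That is 5 to 20 percentage points of the group. It is an upper bound, because it assumes that every site follows the literal rule and that every such ECG is graded clinically significant.

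**The case against.** **The cross-reference.** Both protocol sentences cite Section 6.3.7, and a sensible site would read them together with the definition there. That is a natural reading and may limit the effect. It does not remove the contradiction, because the instruction is not made conditional and the SAP copies point to other sections.

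**Clinical significance.** The ECG rule applies only to abnormalities the investigator grades as clinically significant, and stable atrial fibrillation accepted at entry may not be graded so. This stands as a limit on size.

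**Other safety outputs.** The plan has shifts from baseline in the investigator's ECG assessment (SAP 6.9.4), QTcF thresholds that include change from baseline (SAP 4.2.7), by-visit examination findings (SAP 6.9.6) and medical history of ongoing conditions. Unchanged findings would be visible there, and QTc results do not depend on AE records. This stands: the problem is confined to the AE summaries.

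**Stronger readings a reader might infer.** One is that the treatment-emergent tables are inflated as a matter of course. The documents do not support this: the SAP definition excludes findings that are neither new nor worse, and no section tells sites to date an old finding to the visit. Another is that each post-dose examination or ECG generates a further AE record, so that the count should be multiplied by visits. That is not supported either. An AE has an onset, an end and an outcome (Protocol 6.3.7.2) and is followed until it subsides (6.3.7.3), so a persisting finding can be one continuing record. SAP 4.2.3.1 also counts a preferred term once per participant.

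**Conclusion.** Wrong as written. The contradiction is direct for ECGs and one of principle for examination findings. Followed literally, the rules place unchanged baseline findings in the all-AE summary and possibly in the treatment-related summary. Entry into the treatment-emergent tables needs the further step of a post-dose onset date.

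The size cannot be calculated from the documents. The 3 to 12 men rest wholly on the assumed 5% to 20% and are a ceiling. Any error is towards over-reporting harm. Efficacy results, including the primary endpoint, are unaffected.

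**What to change.** Reconcile the four places (Protocol 6.3.2 and 6.3.3, SAP 4.3.1 and 4.2.7) with the condition already used in Protocol 6.3.7.1 and 6.3.1. Suggested wording: *an abnormality is documented as an AE when it is new or has worsened compared with the last pre-dose finding and meets the definition in Section 6.3.7.* In 6.3.3 and SAP 4.2.7, keep the existing requirement that the ECG be clinically significant. In the SAP, point both sentences to the AE definition instead of to date imputation and AE summaries.

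Unchanged baseline findings stay in the examination and ECG listings and in the shift tables, so nothing is lost from view.

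The cost is one clause in four places. Screening and Day 0 examinations and ECGs are already collected, so no assessment is added. The protocol half needs a formal amendment under Protocol 10.2.

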6.3.3 Triplicate 12-Lead Electrocardiogram

At screening (Visit 1), 12-lead ECG recordings will be obtained in triplicate (within an approximate 2- to 5-minute window) with the participant in a supine position, suitably rested (for at least 5 minutes). At baseline (Visit 2), 12-lead ECGs will be performed in triplicate before administration of the first dose of the IMP; the results should be reviewed by **the cardiologist at the site delegated to review all study ECGs (ie the rater)** to confirm that the participant may be dosed (see Exclusion Criterion Number 8).

Subsequently, triplicate 12-lead ECGs (within an approximate 5-minute window) will be obtained at each dosing visit and at the follow-up visit.

All 12-lead ECGs, including those performed at screening, will be of at least 10-second duration.

The confirmation of the decision regarding the participant's eligibility for the study and all ECGs are to be based on local readings. For evaluation of participants with left bundle branch block, a cardiology consultation is strongly recommended.

At a minimum, interval data (QTcF), ventricular rate, and overall interpretation will be reported for each ECG.

The investigator will record on the eCRF whether the results are normal or abnormal (not clinically significant or clinically significant). If recorded as abnormal and clinically significant, the machine-read results and any clinical interpretations must be incorporated into the eCRF, and, if observed after administration of teverelix TFA, the abnormality must also be documented as an AE (see Section 6.3.7).

6.3.4 Continuous 12-lead Holter Electrocardiogram (Subset of 30 Group 2 subjects)

Continuous 12-lead Holter ECGs will be performed in a subset of 30 Group 2 subjects only (first 30 enrolled subjects with no more than 8 subjects at any one site). Continuous 12-lead Holter data will be obtained from subjects in accordance with time points detailed in the Schedule of Assessments (Table 16).

For analysis of the continuous 12-lead ECG data, triplicate 10 second 12-lead ECGs will be extracted at time points matching certain PK sampling times after at least 5 minutes rest in order to facilitate concentration-QTc effect modelling.

6.3.4 Injection Site Inspection

Each injection site will be visually inspected at each visit for local reactions such as pain, tenderness, erythema/redness and swelling. If the only reaction is induration, this should be indicated on the eCRF and reported as an AE. Any other local reactions will be graded according to the grades mentioned as specified in Table 10 [15] and reported as an AE. Upon complete resolution of an injection site reaction, injection site inspections of that injection site can cease

During the first administration of the injection, an injection site inspection (ISI) will be performed to ensure that the injection site is free from blemishes, tattoos, or other marks that may make subsequent ISIs difficult. ISIs will also be performed at 30 minutes, 4, 12, and 24 hours post-dose. The ISI will be performed at 30 minutes post-dose for all other IMP administration. ISRs will be reported as AEs.

At maintenance dose visits ALL injection sites must be inspected unless an injection site reaction has fully resolved (including induration). For example, at Day 42 the following injection sites should be inspected: D0 SC; D0 IM; D42 SC. And at Day 84 the injection sites for D0 SC; D0 IM; D42 SC; D84 SC should be inspected. Only when an injection site reaction (including induration) has fully resolved can inspection of that injection site stop.

Table 10: Food and Drug Administration Local Toxicity Scale

Local Reaction to	Mild	Moderate	Severe	Potentially
Injectable Product	(Grade 1)	(Grade 2)	(Grade 3)	Life-
				threatening (Grade 4)
Pain	Does not interfere with activity	Interferes with activity or repeated use of non-narcotic pain reliever	Prevents daily activity or repeated use of narcotic pain reliever	ER visit or hospitalisation
Tenderness	Mild pain to touch	Pain with movement	Significant pain at rest	ER visit or hospitalisation
Erythema/Redness ^a	2.5–5 cm	5.1–10 cm	>10 cm	Necrosis or exfoliative dermatitis
Swelling ^b	2.5–5 cm and does not interfere with activity	5.1–10 cm or interferes with activity	>10 cm or prevents daily activity	Necrosis

ER=emergency room

